release, and diurnal variation in adolescents with obesity. **Expand our understanding of the use of CGM in adolescents with obesity.** There is very limited experience of the use of CGM among underserved racial/ethnic minority populations at risk for type 2 diabetes. Current CGM-based metrics provide a clinically meaningful macroscopic perspective on an individual's glycemia. This study aimed to gain data-driven insights from the postprandial glucose response to meal consumption at various times throughout the day to determine if changes in glucose peaks shift by the time of first meal consumption. Results from this study could potentially change the way adolescents with obesity are treated in the future by incorporating meal-timing behaviors as part of their medical regimen.

PROCEDURES INVOLVED

Overview of Proposed Study Design: We propose a cross-over, proof-of-concept study to measure glycemic and metabolic responses to a test meal (controlled for macronutrient profile and caloric amount) administered at various times of the day (early vs. afternoon vs. late) in thirty Latino adolescents (ages 13-19 years), with obesity, without diabetes, to determine how timing of eating impacts glycemic response to the test meal after a 16-h fasting period. All participants will consume three standard test meals administered in random order at different times of day over two-weeks: (1) Early: test meal consumed at 8 AM; (2) Afternoon: test meal consumed at 12 PM; (3) Late: test meal consumed at 4 PM. A continuous glucose monitor (CGM) will be placed on the participant for the duration of the 2-week period. Baseline and post-meal samples will be assayed for glucose, insulin, c-peptide, GLP-1, GIP, PP at times -10, , 10, , 30, , 60, 90, 120, and 180 minutes after glucose. The proposed protocol is modified to include multiple samples during the initial 30 minutes when glucose is rapidly increasing, allowing for modeling of glucose stimulated insulin secretion. The primary endpoints will be glucose, insulin, and C-peptide area under the curve, insulinogenic index, and glucose variability as captured by percent time in range on CGM following the test meal.

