The implementation steps of the proposed RCT are as follows: **(1)** The staff will introduce the study to all eligible participants either in person or virtually and consent interested families for the study; **(2)** All participants and their families will complete baseline study surveys in REDcap; **(3)** All participants and their families will receive training on the use and application of the CGM, which is FDA approved in patients 2 years and older. All equipment required for the duration of the study will be distributed to the participants in-person. **(4)** All participants will be randomized to the order in which they consume their test meal. Test meals will be consumed on different mornings at least three days apart after a 16-h fasting period. Outside of study visits, participants will purchase all their meals as they would normally without alternation to food quality or quantity; **(5)** The study staff will conduct study assessments with participants at baseline and during each test meal study visit (3 total). Participant will be given the option to redo visits with missing lab results (up to 6 total); **(6)** The study staff will perform weekly phone encounters with the participants to assess barriers to study visit attendance and to record any

medication changes or health issues that have occurred in the last 7 days; (7) The PI and research team will meet bi-weekly to monitor all study procedures and oversee data management and analysis.

The implementation steps of the proposed test meals and blood collection are as follows:

- 1) Subjects without a port will have an IV inserted;
- 2) -10 min pre-meal blood sample (5 mL) will be collected from the port or IV for fasting labs;
- 3) Subjects will consume meal; and
- 4) 10 min post-meal blood sample (5mL), 30 min post-meal blood sample (5mL), 60 min post-meal blood sample (5mL), 90 min post-meal blood sample (5mL), 120 min post-meal blood sample (5mL), and 180 min post-meal blood sample (5mL) will be collected from the port or IV post-meal test.

Sharing of Testing Results with Subjects

Study endpoints will be shared with participants upon request via email or over the phone. The PI will review any tests results and if additional medical evaluation is warranted will refer to the primary care providers.

Study Timelines

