Quantifying incretin hormones after test meal from venous sample: Following baseline sampling (0 min), a test meal will be administered. glucagon, GLP-1, GIP, and PP concentrations will be measured in duplicate from plasma samples using Millipore Enzyme-linked Immunosorbent Assays (ELISA) or multiplex assays according to the recommendations of the manufacturer (Birmingham, MA). Total area under the curve (AUC) will be calculated for venous glucagon, GLP-1, GIP, and PP concentrations using the trapezoid methods using GraphPad Prism (Version .01, GraphPad Software Inc, San Diego, CA, USA).

Statistical Consideration: The sample size estimates, and analytical plans were developed under the guidance of [name] who is the Director of the TSRI Biostatistics core and who will also be a mentor on this award. Descriptive statistics, including graphical depictions, will be utilized to assess the degree of symmetry/normality of continuous outcomes and identification of outliers. A ladder of powers approach will be applied to identify the best easy-to-interpret transformation of the continuous outcome variable. The statistical approach will be implemented with and without transformations when appropriate. Data for this 3-treatment, 3-period cross-over design will be analyzed using linear mixed effects model as described in the literature and implemented in STATA 17.1 (College Station, TX) Sensitivity analysis applying weighted least squares regression will follow. Areas under curves (AUC) will be calculated by the trapezoid rule for levels after meal ingestion. Separate AUC will be calculated for the early (initial 30-min) and the total (entire 300-min) responses. This separation of responses in early and total was decided based on previous findings that insulin secretion is progressively increased during these first 30 min after oral nutrient ingestion. Wilcoxon matched paired test will be used for tests of significance between variables obtained during morning, afternoon, and evening meal ingestion. Spearman regression coefficients will be obtained to estimate correlation.

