commercial weight management programs already available and used by youth with obesity that incorporate time-based recommendations. The long-term goal of this research is to generate knowledge regarding how time-based dietary programs can benefit pediatric patients with obesity. This work can inform the development of potentially low-cost, scalable, and sustainable interventions to optimize treatment recommendations for this high-risk population.

Costs to Subjects

There will be no cost to subjects. Subjects will not be accountable for any research costs.

Consent Process

The implementation steps of the proposed randomized controlled trial (RCT) are as follows:

1. Study staff will introduce the study to all eligible subjects and recruit and consent interested families.
2. All participating subjects and their parent/legal guardian/family member will receive training on the use, application, and equipment for CGM. All equipment required will be distributed to the subject, and they will download the Dexcom app onto their personal smartphone setting up an account with a codename.
3. Consented participants wear the CGM prior to being randomized to begin with one of three meal times (Early: test meal consumed at 8 AM; Afternoon: test meal consumed at 12 PM; Late: test meal consumed at 4 PM (<30% protein, 10% fat, and 60% carbohydrates [CHO]) + blinded CGM.
5. The study staff will conduct in person/virtual study assessments of subjects and their parent/legal guardian/family member at 3 time points throughout the study period.
6. The study staff will perform weekly calls to assess barriers to adherence, review CGM data and perform dietary recall.
7. The principal investigator (PI) will complete and oversee data management and analysis.

Schedule of Study Procedures	Visit 0	Visit 1	Visit 2	Visit 3
Study Visit	Consent Visit	Day 1	Day 7	Day 14
Study Window	NA	+/-7 days	+ /- 7 days	+ /- 7 days

**Consent Session	X			
Randomization in mealtime assignment	X	X		
Weight and height measured		X	X	X
**CGM Use and Data Review:	X	X	X	X
Time in range	X	X	X	X
Education and equipment	X			
CGM Placed	X			
**24-hour Dietary Recall Collection		X	X	X
Research blood draw/fasting labs: glucose, insulin, c-peptide, glucagon, GLP-1, GIP, PP: -10, minutes.		X	X	X
Lab Testing: at post-meal samples glucose, insulin, c-peptide, glucagon, GLP-1, GIP, PP		X	X	X
Meal Test: 10, , 30, , 60, 90, 120, , 180 minutes		X	X	X
**Surveys		X	X	X

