initial recruitment process, a follow-up phone call will be made by a trained recruiter within one week to answer questions and solicit participation. Consent can be withdrawn from at any time. Potential participants will have the following carefully explained: (1) the investigational nature of the research; (2) the objectives of the research; (3) the procedures involved in the research; (4) any and all risks and discomforts due to participation; and (5) alternative options to participation that are currently available. Clarification questions will then be elicited from the potential participants and their parents/guardians. Only after the above will an IRB-approved document recording informed consent be signed as per institutional guidelines with a copy to be given to the participant and the original stored with the research record in a secure location. Data protection will be ensured by storing on an IS-approved university database on encrypted servers. All participants will be issued a study ID with data entered in de-identified manner. All databases will be password-protected with access only to the study team. All paper/documentation/research charts will be maintained in locked locations accessible only to the study team.

The IRB has strict regulations for the approach to and documenting of assent by minors and consent by their parents/guardians. Documentation of assent/consent is done via IRB-approved study-specific forms.

Setting

- All research procedures will be conducted in Children Hospital Los Angeles (Los Angeles, CA).
- The USC DORI may be utilized to collect study endpoints. At USC, study staff may complete study procedures during visits 1, 2, and 3 (refer to the **Schedule of Study Procedure table**). Additionally, research blood draws (baseline and post-meal samples will be assayed for glucose, insulin, c-peptide, GLP-1, GIP, PP at times -10, , 10, , 30, , 60, 90, 120, and 180 minutes after glucose) will be completed.

Resources Available

References:

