Mixed-effects linear regression model was used to assess changes in glucose, insulin, and c-peptide profile over the course of 180 minutes and the difference of first mealtime at 8:00AM, 12:00PM, and 4:00PM univariately. The difference of mealtime over the course of 180 minutes on glucose, insulin and c-peptide levels was assessed by including mealtime as an interaction term in the mixed-effects linear regression model. Due to the skewness of the distribution, differences in glucose, insulin, and c-peptide AUCs over 180 minutes and the insulinogenic index by mealtime were assessed on a logarithmic scale. Profiles that were significantly differ across meal timing were subjected to pairwise comparisons using the false discovery rate based on Simes' method. Changes in profiles were described using beta estimates (β) with its associated 95% confidence intervals and p-values. Pairwise comparisons were presented as percent changes with its associated 95% confidence intervals, unadjusted and adjusted p-values.

The secondary outcome variables included incretin levels and pancreatic hormones, which includes glucagon, pancreatic polypeptide, glucagon-like-peptide-1 (GLP-1), and glucose-dependent-insulinotropic polypeptide (GIP). Mixed-effects linear regression model was used to assess the changes in incretin levels and pancreatic hormones between pre- and post-intervention timepoints. Additionally, mealtime difference on the changes in incretin levels and pancreatic hormones was assessed by including an interaction term in the model, and these variables were analyzed on logarithmic scale. The distributions of incretin levels and pancreatic hormones were described in median and interquartile range by pre- and post- intervention timepoints. The paired difference of pre and post was described using median and 95% confidence intervals by mealtime. Statistical significance was set at 0.05 with two-sided test and all statistical computations were performed in Stata/SE 18.0 (StataCorp, College Station, TX).

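### The protocol commits to trapezoid AUCs for glucagon, GLP-1, GIP and PP, but the SAP names only a pre-to-post change in these hormones and leaves 'post' undefined

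*Combined protocol and SAP*

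**What the plan says.** **Promised measure.** The Aim 2 part of the protocol's Measurements section, in the paragraph on incretin hormones, states: "Total area under the curve (AUC) will be calculated for venous glucagon, GLP-1, GIP, and PP concentrations using the trapezoid methods".

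**Samples.** The blood-collection steps under Procedures Involved list a draw at −10 min and post-meal draws at 10, 30, 60, 90 and 120 min, ending with "180 min post-meal blood sample (5mL) will be collected from the port or IV post-meal test". The Schedule of Study Procedures puts all four hormones on the −10 min draw at Visits 1 to 3, and lists for the later draws: "at post-meal samples glucose, insulin, c-peptide, glucagon, GLP-1, GIP, PP".

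**Model.** Statistical Consideration says: "Data for this 3-treatment, 3-period cross-over design will be analyzed using linear mixed effects model". It points to the literature and lists no model terms.

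**SAP.** The closing Statistical analysis section gives glucose, insulin and c-peptide two analyses: a mixed model of the 180-minute profile with a mealtime interaction, and a log-scale comparison of AUC over 180 minutes. For the four hormones it says: "Mixed-effects linear regression model was used to assess the changes in incretin levels and pancreatic hormones between pre- and post-intervention timepoints". It adds a mealtime interaction on that change (log scale), medians and interquartile ranges before and after, and a paired pre/post difference by mealtime.

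**Hypothesis.** Aim 2 in Specific Aims predicts a greater change in these hormones after the 12 PM and 4 PM meals than after the 8 AM meal. It names no sampling time.

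**The concern.** The SAP does not name the measure that the protocol commits to for Aim 2, and nothing says that the measure was dropped or why. What replaces it cannot be reproduced from the text: with six post-meal samples on the schedule, 'post' could be any one of them, or a summary of several.

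The study asks whether clock time alters the response to a meal. One way that could happen is through an earlier or later hormone peak. In that case a pre-to-post contrast taken at one sample mixes the timing of the response with its size, and two analysts using different samples could report different mealtime effects from the same data.

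**Working it through.** The plan gives no power, sample-size or alpha calculation for the hormones, so there is no figure of its own to reproduce. The check is a comparison of texts with a little arithmetic.

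**1. Side by side**

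| Item | Glucose, insulin, c-peptide | Glucagon, GLP-1, GIP, PP |
|---|---|---|
| Scheduled samples per visit | 1 pre, 6 post | 1 pre, 6 post |
| AUC in the protocol | yes | yes |
| AUC over 180 min named in the SAP | yes, log scale | no |
| 180-min profile by mealtime named in the SAP | yes | no |
| Pre-to-post change named in the SAP | not needed | yes, 'post' undefined |

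**2. Values used.** Scheduled values per visit: 1 + 6 = 7. If 'post' is one sample, two are used and 7 − 2 = 5 are not. This figure is conditional on that reading.

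**3. A one-sample change is not the promised AUC.** With the pre-meal value placed at 0 min, the trapezoid weights for samples at 0, 10, 30, 60, 90, 120 and 180 min are 5, 15, 25, 30, 30, 45 and 30 min, summing to 180. One post-meal sample therefore carries between 15/180 = 8.3% and 45/180 = 25.0% of the total weight. With the pre-meal value kept at −10 min, the first two weights become 10 and 20, the sum is 190, and the range is 20/190 = 10.5% to 45/190 = 23.7%.

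**4. Does the choice of sample matter? (illustration only)** The documents contain no hormone curves. Assume y(t) = 10 + A·(x·e^(1−x))², with x = t/tp, and a reference meal with tp = 30 min and A = 20. Both meals start at 10, so the mealtime contrast in log pre-to-post change is ln(y_comparison / y_reference) at each sample.

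| Comparison meal | 10 | 30 | 60 | 90 | 120 | 180 min | AUC0-180 ratio |
|---|---|---|---|---|---|---|---|
| Peak at 45 min, same height | −0.228 | −0.094 | +0.305 | +0.449 | +0.334 | +0.073 | 3428/2887 = 1.187 |
| Peak at 30 min, rise 50% larger | +0.206 | +0.288 | +0.231 | +0.117 | +0.036 | +0.002 | 3430/2887 = 1.188 |

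In the first row the curves cross at ln(1.5)/(1/30 − 1/45) = 36.5 min, so the sign differs before and after. In the second row the sign never changes, but the size runs from 0.002 to 0.288. The two rows have almost the same AUC ratio, so AUC summarises the total response and does not show timing.

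**5. Two related inconsistencies.** Statistical Consideration also says: "Separate AUC will be calculated for the early (initial 30-min) and the total (entire 300-min) responses". Sampling ends at 180 min, so (300 − 180)/300 = 40% of that interval has no sample. The SAP already uses 180 minutes for glucose, insulin and c-peptide. Separately, the Overview of Proposed Study Design says "Baseline and post-meal samples will be assayed for glucose, insulin, c-peptide, GLP-1, GIP, PP at times" and then gives the sampling times; the Setting section repeats the list. Both leave out glucagon, which Aim 2, the schedule and the SAP include.

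**The case against.** The best defence is that Aim 2 is worded as a greater change, and the SAP tests exactly that with a mealtime interaction on a change. This stands as far as it goes: the change is a legitimate measure and should be kept. It does not say which sample is 'post', and it does not withdraw the AUC commitment.

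A second defence is that the SAP speaks of timepoints in the plural, so all post-meal samples may be in the model. That is possible, but the paired pre/post difference suggests a single pair. With two readings open, the analysis is not specified.

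Third, a full hormone profile model is promised nowhere, and the curves in the illustration are assumed. Both points stand. The profile model can only be an option, and the sign change is a consequence of assuming a shifted peak, not evidence that one occurs.

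A reader might also infer more than the text supports:

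- *That 'post' was picked after the results were seen.* The SAP is in the past tense, but the documents do not show when the choice was made.
- *That the hormones may not have been assayed*, since the Blood Collection paragraph names none of the four. The same paragraph has DPP-4 and aprotinin inhibitors added to the tubes, which suggests that peptide assays were intended, and the hormones are named in Aim 2, the schedule and the SAP.
- *That the primary result is affected.* It is not: the SAP specifies AUC and profile analyses for glucose, insulin and c-peptide.

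**Conclusion.** The point holds. The promised hormone AUC is missing from the SAP without explanation, and the measure that takes its place is not defined. Confidence is high, because the conclusion rests on complete sentences in both texts and not on the illustration.

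Its reach is limited to the interpretation of Aim 2. How far a mealtime contrast would move with the choice of sample cannot be stated from the documents. It could be little if the hormone curves keep their shape and timing across mealtimes and the sample lies near the peak, and it could change sign if the peak shifts. The count of five unused values holds only if 'post' means one sample. This should be corrected, but it is not a flaw in the trial's main comparison.

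**What to change.** 1. Analyse log AUC0-180 of each hormone by mealtime, in a crossover linear mixed model. Since the protocol lists no terms, mealtime, period and a participant random intercept are this review's proposal. Handle fasting window (Potential Challenges and Alternative Approaches, item 3) and puberty (Inclusion Across the Lifespan) as the protocol states. Use total AUC, as the protocol says; any baseline-adjusted or incremental AUC is a sensitivity analysis.
2. State which sample or summary is 'post', and keep the pre-to-post change as a supportive analysis.
3. Optionally, apply the SAP's time-by-mealtime model to the hormone samples to show timing.
4. Use the SAP's false discovery rate method for pairwise comparisons: up to 4 hormones × 3 pairs = 12 for the AUCs, and up to 24 if the profile model is also compared.
5. If some times were not assayed, or the analysis is already done, disclose the departure, label the additions as made to meet the protocol, and limit the Aim 2 conclusion to the times measured.
6. As a tidy-up, reconcile the 300-minute total AUC with sampling that ends at 180 min, and add glucagon to the timed assay lists in the Overview and Setting sections.

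**Cost.** One derived variable and one model per hormone (four models, or eight with the optional profile model), and one line to define 'post'. No new samples are needed if the scheduled ones were assayed. If they were not, AUC0-180 may not be recoverable, and only the definition and the disclosure apply.
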